### Clinical Trial/GCP Training

*Is this a research study in which one or more human subjects are prospectively assigned to one or more biomedical or behavioral interventions (which may include placebo or other control) to evaluate the effects of those interventions on health-related biomedical or behavioral outcomes (i.e a clinical trial)? Indicate “yes,” “no,” or “N/A” in the space immediately below.*

Yes.

*Is the study fully or partially funded by the NIH? Indicate “yes,” “no,” or “N/A” in the space immediately below.*

Yes.

*Have the required key personnel completed Good Clinical Practice (GCP) Training? Indicate “yes,” “no,” or “N/A” in the space immediately below. (Note that IRB approval will not be given for NIH funded clinical trials until all required key personnel complete the GCP training.)*

Yes.

### Research Plan

***Purpose/Introduction:*** [State the reason for the study, the research hypothesis, and the goals of the proposed study as related to the research question(s). Provide a clear and succinct summary description of the background information that led to the plan for this project. Provide references as appropriate and, when applicable, previous work in animal and/or human studies. Provide previous UConn protocol number, if applicable.]

Please note that this protocol is for the pilot trial, aim 3, in the grant application SPS 180816 “Using a Narrative-Based Approach to Reducing Indoor Tanning”. The development phase, aims 1 and 2, was submitted and approved under protocol # H17-305.

**Indoor tanning is a risk factor for the most prevalent cancer in the US.** Skin cancer is the most prevalent cancer in the US, and incidence of melanoma, the deadly form, has doubled since 1973. A recent study revealed we now have more cancers related to indoor tanning than tobacco. Indoor tanning increases risk for melanoma, which is, as a result, the most common cancer in women aged 25-29. A population-based study of US adults

---

The term “prospectively assigned” refers to a pre-defined process (e.g., randomization) specified in an approved protocol that stipulates the assignment of research subjects (individually or in clusters) to one or more arms (e.g., intervention, placebo, or other control) of a clinical trial.

An intervention is defined as a manipulation of the subject or subject’s environment for the purpose of modifying one or more health-related biomedical or behavioral processes and/or endpoints. Examples include: drugs/small molecules/compounds; biologics; devices; procedures (e.g., surgical techniques); delivery systems (e.g., telemedicine, face-to-face interviews); strategies to change health-related behavior (e.g., diet, cognitive/behavioral therapy, exercise, development of new habits); treatment strategies; prevention strategies; and, diagnostic strategies.

 3. Health-related biomedical or behavioral outcome is defined as the pre-specified goal(s) or condition(s) that reflect the effect of one or more interventions on human subjects’ biomedical or behavioral status or quality of life. Examples include: positive or negative changes to physiological or biological parameters (e.g., improvement of lung capacity, gene expression); positive or negative changes to psychological or neurodevelopmental parameters (e.g., mood management intervention for smokers; reading comprehension and /or information retention, behavioral intervention for psychiatric symptoms); positive or negative changes to disease processes; positive or negative changes to health-related behaviors; and, positive or negative changes to quality of life.

found that 6.5% of women and 1.7% of men have tanned indoors in the past year. However, young women have the highest rates (14%). A recent study revealed that 20% of college students had used a tanning bed in the last year. In 2014, the Surgeon General's Call to Action to Prevent Skin Cancer emphasized the need to reduce harms from indoor tanning with targeted messaging efforts.

**Health messaging doesn't work.** In a recent study, 99% of indoor tanner surveyed were aware that tanning can cause skin cancer and premature aging, which suggests that educating tanners about the risks is not changing behavior. The majority (83%) of participants agreed that tanning makes them more attractive and 83% said tanning helps them relax. The immediate desirable consequences of tanning seem to override concerns about future consequences to health. Researchers have moved toward messaging related to the appearance-damaging effects of UV exposure (e.g., premature skin aging and wrinkling) in combination with health risk messaging, with modest results. Two limitations of previous research are 1) appearance messaging still focuses on long-term consequences (e.g., wrinkles) and 2) researchers pay tanners to review intervention content which lacks real world applicability. Interventions that persuasively increase the salience of the negative immediate consequences of tanning and in a way that engages tanners might be more impactful. Our proposal addresses these issues.

**Tanners' tweets reveal immediate negative consequences.** Our previous research shows that women who tan indoors use social media at higher rates than their peers. We content analyzed 1000 tweets that included the words "tanning bed" or "tanning salon." Most of these tweets (71%) clearly indicated the user engaged in indoor tanning. Many tweets (57%) expressed positive sentiment about tanning, but 31% described negative experiences including unexpected burns, deceptive business practices, injuries (e.g., swollen eyes), bad odors, unsanitary conditions, and peeping Toms. Incorporating narratives about these everyday negative tanning salon experiences in an intervention may more effectively impact tanning than an intervention that focuses on long-term consequences. Negative experience narratives could shift attitudes around the desirability of tanning by associating tanning with real life imagery that generates disgust (i.e., unsanitary conditions), distrust (i.e., deceptive practices), and anxiety (i.e., being spied on while naked). This is consistent with recent laboratory-based research that showed that graphic and loss-framed messages are effective in increasing tanner's motivation to quit.

We recently conducted focus groups of 15 tanners to explore messaging they would find compelling. They urged us against both health and appearance messages but instead to capitalize on content that would make them angry or rebellious, and they specifically mentioned tanning salon deceptive practices. We propose an intervention that uses real negative experience tweets by tanners as conversation starters about the costs vs benefits of tanning. To balance the negative, we will also include tweets that share the positives of quitting tanning and using UV alternatives like spray tans or bronzing makeup in an effort to shift attitudes about these. Tanners who see similar others making the decision to quit or switch to alternatives might be moved to follow suit. Our first aim is to identify search terms with high precision for identifying this content on Twitter so that it can be leveraged in the intervention.

**Transportation theory as a framework for persuasion.** Transportation theory suggests that one's behavior is governed by stories about one's life, and to the extent that a person is transported into a narrative or story, it can affect their beliefs. Young adults convey personal stories to their social media audience every day. These narratives may be more persuasive than conventional messages from organizations/professionals because when individuals identify with characters in a story the narrative shifts their thinking and behavior. Research also reveals that the persuasive impact of social media posts in young adults is associated with how similar the user perceives themselves to be to the individual who made the post.

**Social marketing theory as a framework for engagement.** Social marketing theory is a framework to design, implement, and evaluate social media-delivered content. Social marketing theory suggests that effective campaigns must package information in a manner that will be accessible, digestible, and engaging to a target audience. Social media facilitates audience awareness via repeated messaging, i.e., "saturation." Image advertising is used and involves pairing a "product" with recognizable images and ideas to create a favorable setting for product promotion. Image advertising stimulates audience interest which increases the likelihood that

new information will be consumed. Using this theory as a guide, a Twitter feed will be created that includes content from sources recognizable to the target population (e.g. magazines, fashion blogs).

**Real world implementation plan via the Skin Smart Campus Initiative.** The PI is co-chair of the *Indoor Tan-Free Skin Smart Campus Initiative*, a program modeled after the *Tobacco Free Campus Initiative*, and commissioned by the National Council for Skin Cancer Prevention in 2016 (See Letter of Support). Our mission is to encourage universities to adopt a policy that prohibits tanning beds on campus, severs relationships with tanning businesses (e.g., as cash card vendors), and provide education to their student bodies. Three universities (total enrollment= 70,775) have already adopted the policy-- East Tennessee State University, University of North Florida, and Temple University (pending). Our team is actively engaging others with a goal of >2-3 campuses/year. We have an opportunity to leverage these relationships to engage their students in a social media feed produced by this line of work. To remain in good standing as a Skin Smart Campus, they must provide education and this feed is how we can help them accomplish that goal. We have a letter of support co-signed by our current campuses showing their support for our mission of eventually using this feasibility work to inform a randomized trial, followed by an implementation plan targeting their campuses.

### **Preliminary Studies.**

**Team.** Our interdisciplinary team is well-equipped to do this research by including a behavioral scientist with expertise in skin cancer prevention and social media delivered interventions, an epidemiologist/biostatistician with experience analyzing social media data, a computer scientist with experience analyzing social media data, and a dermatologist with media messaging experience.

**What messaging strategies do indoor tanners find compelling?** Female tanners (N=15; 87% Caucasian; mean age=22) participated in 2 focus groups conducted by [name] (consultant) with consultation from the PI. Tanners were asked to discuss the credibility of various message sources (e.g., peers, celebrities, public health organizations), to suggest persuasive messaging approaches, and critique a set of messages. Tanners said they have more trust in messages coming from peer or celebrities than from organizations like American Cancer Society. They avoid messaging that makes them sad (e.g., narratives about cancer deaths), or that attempt to exert control over their behavior (e.g., restrictions/laws). They preferred messages that make them feel in control and those that generate anger and defiance such as those focusing on shady industry tactics as long as they are factual.

**Do tanners tweet about their tanning? Study 1:** We used the Twitter Streaming API to collect in real time all tweets mentioning indoor tanning, tanning bed, tanning booth, tanning salon, sun bed, or sunlamp, over 2 weeks. Over 154K tweets mentioned indoor tanning, or 7.7 tweets per minute, suggesting this is an oft tweeted topic.

**Study 2:** All tweets in 2013 containing search terms for both indoor tanning (e.g., tanning bed) and burns (e.g., burn, fried) were extracted by a social media monitoring firm (Olytico; Dublin, Ireland). Each tweet was assessed to determine whether an indoor tanning burn is described. A total of 16,827 described indoor tanning burns. Tweets included descriptions of peeling (n=53), blistering (n=10), skin purpling (n=12), as well as inability to sleep (n=125), sit (n=103), or move (n=85). Findings reveal that reports of tanning bed burns/injuries are plentiful on Twitter. **Study 3.** We used NVivo to extract unique tweets using the terms “tanning bed” or “tanning salon” over a 7-day period (N=4,691) to learn about the full range of experiences tanners report. We randomly selected 1,000 tweets for content analysis. Tweets (n=1,000) were posted by 978 unique accounts. The majority of tweets (71%; N=699) were clearly by tanners. Themes included: tanner expressing positive sentiment about tanning (57%), tanner sharing a negative experience (32%), and tanner reporting sleeping in a tanning bed (9%). Negative experiences included burns/injuries, unsanitary conditions, poor results, being lied to by employees about pricing or likelihood of getting burned, and privacy violations (e.g., being walked in on while unclothed).

**Aim:** We will conduct a pilot randomized feasibility trial (N=60) comparing a 1 month sun safety social media intervention to a healthy lifestyle social media intervention. Our outcomes include recruitment, retention, acceptability, participation, message engagement (likes, replies), and message dissemination (retweets, shares, impressions). We will describe changes in outdoor tanning, unprotected sun exposure, sun protection (sunscreen, protective clothing), burns, tanning intentions, and desirability of a tan during the one month intervention period as exploratory outcomes.

**For EACH Participant Population State the Number of Participants to be Enrolled and Screened and/or the number of participant records reviewed (including, HIPAA covered health records and FERPA covered school records), if applicable:** [State the total number of participants/records to be enrolled and, if enrolling more than one participant population, describe the total enrollment for each. Tip: consider attrition and the number of participants who may fail screening. Use of a range may provide flexibility. Note that the range must be justified in the **Justification of Sample Size section below.**]

We plan on enrolling 60 indoor tanners to complete the pilot trial. Since we are recruiting online, we anticipate screening a total of 1000 participants to achieve this goal. Since the initial contact is via an online link, there will be many incomplete responses driving up the number of screened-out participants.

**Justification of Sample Size:** [For qualitative and pilot studies, describe how the proposed sample size is appropriate for achieving the anticipated results. For quantitative studies, provide a power analysis that includes effect size, power and level of significance with references for how the sample size was determined. Explain the rate of attrition and possible number who fail the screening, with references as appropriate.]

The purpose of this pilot is to assess intervention feasibility. Leon, Davis, & Kraemer (2011) state “power analyses should not be presented in an application for a pilot study that does not propose inferential results”. As they and others recommend, we based a sample size of 30 per group on necessities for examining feasibility.

**For EACH Participant Population State Describe the Study Population(s):** [Describe the participant population(s) including gender, ethnicity, income, level of education and age range.]

We are recruiting women and men in the United States who are ages 18-30, report to have used tanning beds at least once in the past year, are likely to tan outdoors this summer, and who is a regular user of any social media platform (on most days of the week).

**Enrollment of UConn Students and/or Employees:** [Will UConn students be enrolled? If so, describe if these students include those who any key research personnel teaches, or for whom any key research personnel has responsibility. Will UConn employees be enrolled? If so, describe if these employees report to any key personnel. For each group, explain why this population is necessary to the study. Tip: convenience is not sufficient justification.]

We will be recruiting women and men 18 and 30 from states in the US that have an averages temperature of  $\geq 75$  degrees in May. UConn students and employees may be enrolled if they meet eligibility requirements and are interested in completing the study. Since it is not essential that we recruit students and employees directly reporting to key personnel on this project, we will exclude them from participation.

**Enrollment of Key Personnel, Spouses or Dependents/Relatives:** Will study key personnel, spouses of key personnel, or dependents/relatives of any key personnel be enrolled in the study? If so, describe and provide justification.

No.

**For EACH Participant Population Describe Recruitment Methods:** [Specify each method and describe specific procedures for how participants will be identified and recruited. Attach copies of all advertisement/recruitment materials for IRB review. Describe how UConn Students/Staff and Key Personnel/Spouses/Dependents/Relatives will be identified and recruited, if applicable.]

We will focus our recruitment in locations that have an average temperature  $> 75$  in May. These states include: California, Arizona, Oklahoma, Texas, Alabama, Arkansas, Florida, Georgia, Kentucky, Louisiana, Maryland, Mississippi, North Carolina, South Carolina, Tennessee, Virginia, West Virginia, Kansas, Missouri, Delaware, and Hawaii. A survey link will be included with our recruitment materials. Participants will be instructed to complete the survey to be considered for the study and will be recruited using the following online strategies:

- Google ads that appear when users search the words related to tanning;
- Social media posts on Facebook, Instagram, and Twitter;
- Connect with large businesses to get our ad and/or flyer emailed to their staff and students;
- Posts on Craigslist
- Other online sources as appropriate
- Having participants refer their friends and/or family in the study

Recruitment ads will describe the study based on the topic of interest (e.g. beauty) and will employ strategies for attracting tanners as suggested by focus groups.

A portion of our participants will be recruited from Qualtrics, a recruitment panel company. These participants will also complete the initial survey required for eligibility. Emails of eligible participants will be given to our staff from Qualtrics along with their initial survey data.

- On the first page of the survey, they will read a brief introduction about this project and if they complete the survey, they will receive Qualtrics incentives regardless of participation in this trial.
- If they decide to hear more, they will click forward to the next page, which will be our information sheet.
- If they would like to participate in the trial after reading that sheet, they will click forward to the next page and start the survey.
- Participants who provide their email will be contacted by the study team for the telephone screening.

**For EACH Participant Population Describe Screening Procedures, if applicable:** *[Describe when participants will be screened and how this will occur. Include copies of all screening forms and related documents. Describe procedures to notify participants of the screening result, if applicable. Provide a copy of the screening instrument.]*

Participants will complete screening procedures online and over the phone since they will be non-local to UConn. We will focus our recruitment in locations that have an average temperature > 75 in May. These states include: California, Arizona, Oklahoma, Texas, Alabama, Arkansas, Florida, Georgia, Kentucky, Louisiana, Maryland, Mississippi, North Carolina, South Carolina, Tennessee, Virginia, West Virginia, Kansas, Missouri, Delaware, and Hawaii.

We will post online recruitment ads which will contain a link to an online 5-minute survey containing the initial screening questions. The survey will first have a description of the study and will then have the eligibility questions. The participants recruited by Qualtrics will also complete this initial survey. If they are eligible to proceed they will be contacted by the study team to book a 10-minute telephone screening call to review the consent. Afterwards they will be emailed a 15-minute online baseline surveys including tanning behavior, sun protection behavior, and social networking use. Participants will be randomized into two conditions, one will be assigned to a sun safety challenge and the other will be assigned to a healthy lifestyle through technology challenge.

**Anticipated Study Time Frame:** *[Describe the estimated time frame of the study from anticipated start to anticipated finish. If the study will occur in more than phase include these in the time frame. Use of a table is often helpful.]*

This study will take approximately 2 hours of time for participants to complete according to the breakdown below:

Visit	Time (in minutes)
Initial Survey	5 min
Telephone Screening	10 min
Baseline survey	15 min
Webinar	30 min

Intervention Approx. 10-15 min/week for 4 weeks	60 min
Follow-up survey	30 min
Total	2.5 hours

**Design, Procedures, Materials and Methods:** *[Describe the study design, including the sequence of study procedures. Experimental procedures should be clearly described and labeled as such. If the study uses control or experimental groups, or different treatment arms, clearly describe what participation will be like for each of the groups or study arms. Tip: describe procedures in the order conducted, where they will be conducted and how long they will take to complete. The IRB strongly suggests that investigators incorporate flexibility into the study design to accommodate anticipated events (i.e. explain how missed study appointments can be made up by participants). If this study offers treatment for the participants' condition, complete the Treatment Study Supplemental Form (IRB-1C) and attach it to this application for review. Use of a table is often helpful here.*

**Study design:**

Overview: Participation starts with an initial survey, telephone screening, and baseline survey. Eligible participants will then be randomized to one of two conditions, complete a webinar, 4-week intervention, and an end-of-study follow-up survey.

About the intervention: During the 4-week intervention, participants will be asked to create social media posts (related to the topic of the condition). These posts will be sent to the study team who will post them in our study-lead Twitter and Facebook feeds. The sun safety challenge posts will be posted in the Skin Smart Campus Initiative feed and the healthy lifestyle through technology challenge posts will be posted in the @UConnmHealth Feed.

**Randomization:**

Randomization will take place after eligibility is determined and screening procedures are complete. Using the pre-programmed randomization feature in REDCap, participants will be randomized to the sun safety challenge condition or the healthy lifestyle through technology challenge stratified by gender and US region (West, Southwest, Southeast, Midwest, and Northeast). The program director will tell the research assistants who will reach out to participants to inform them of the condition assignment.

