### Statistical Analysis Plan

We summarized recruitment, retention, participation, acceptability, contamination, motivation, belief that a tan is attractive, tanning intentions, outdoor tanning, sun protection behaviors, post engagement, and persuasive impact of posts using descriptive statistics. Means and standard deviations (M[SD]) were presented for variables that were normally distributed, and medians and inter-quartile ranges (IQR) were presented for variables that were not. We compared retention, participation, and acceptability rates to our pre-determined benchmarks of >80% as a metric of feasibility. We compared perceived change in motivation for each target health behavior, intentions to outdoor tan, and number of times tanned outside by condition using Wilcoxon rank sum tests as these variables were not normally distributed. We also compared if participants outdoor tanned at follow-up using a chi-squared test. As this pilot feasibility trial was not sufficiently powered to establish efficacy on the belief that a tan is attractive or sun protection behaviors, we did not compare conditions on these variables. Data analyses were conducted using SAS 9.4 (SAS Institute, Inc, Cary, NC).

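### Randomisation is stratified by gender and US region, but the SAP's Wilcoxon and chi-squared tests ignore the strata without a stated reason; stratifying by gender is a minor, nearly free improvement

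*Protocol*

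**What the plan says.** **Design.** The protocol's Randomization section says that "participants will be randomized to the sun safety challenge condition or the healthy lifestyle through technology challenge stratified by gender and US region", and it names five regions. With two gender levels and five regions that is at least ten cells. Allocation is done "Using the pre-programmed randomization feature in REDCap"; the block size is not given. The Aim paragraph sets the scale: "We will conduct a pilot randomized feasibility trial (N=60").

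**Analysis.** The SAP compares perceived change in motivation, intentions to tan outdoors and "number of times tanned outside by condition using Wilcoxon rank sum tests as these variables were not normally distributed". For the binary outcome it says: "We also compared if participants outdoor tanned at follow-up using a chi-squared test". It mentions no stratified version, no covariate and no reason for omitting the strata. The t-tests in the protocol's Data Analysis section are unadjusted too.

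**Sample size.** Under Justification of Sample Size, "we based a sample size of 30 per group on necessities for examining feasibility". That section cites the advice that "power analyses should not be presented in an application for a pilot study that does not propose inferential results". Neither document states an alpha level, a power or an effect size.

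**The concern.** Stratified allocation forces the arms to be nearly balanced on gender and region. If those factors predict the outcome, the difference between arms varies less from trial to trial than it would under simple randomisation. A test that ignores the strata still leaves the between-stratum variation in its error term. Its standard error is then too large, its true type I error falls below the nominal level, and it detects real differences less often than the design allows.

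With at most 60 participants, a needlessly conservative test could make a signal look weaker than it is, and the protocol intends this pilot to inform a larger efficacy trial. The sample-size section leans on advice for pilots without inferential results, yet the SAP does run tests. If tests are to be reported, they should reflect how participants were randomised.

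**Working it through.** **Inputs from the documents.** N = 60, 30 per arm; strata of gender and five regions; unstratified Wilcoxon and chi-squared tests; a retention benchmark above 80%. There is no power figure to reproduce.

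**Inputs assumed.** Two-sided 5%, permuted blocks of 4, and a range for R², the share of outcome variance explained by the strata.

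**Step 1: direction and rough size (large samples, perfect balance).** With z = 1.960 and ncp = d/√(2/30):

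- True size of the unadjusted test: 2 × [1 − Φ(z/√(1−R²))]
- Power, unadjusted: Φ((ncp − z)/√(1−R²))
- Power, adjusted: Φ(ncp/√(1−R²) − z)

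Take d = 0.736, so ncp = 0.736/0.2582 = 2.850, and R² = 0.10, so √(1−R²) = 0.9487:

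- Size = 2 × [1 − Φ(2.066)] = 0.039
- Power, unadjusted = Φ(0.939) = 82.6%
- Power, adjusted = Φ(1.045) = 85.2%, a gain of 2.6 points

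| R² | Size, unadjusted | Power gain from adjustment |
|---|---|---|
| 0 | 0.050 | 0 |
| 0.05 | 0.044 | 1.3 points |
| 0.10 | 0.039 | 2.6 points |
| 0.20 | 0.028 | 5.0 points |
| 0.30 | 0.019 | 7.0 points |

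**Step 2: gender-stratified Wilcoxon at this sample size.** Two sets of simulated trials, A and B, were run with 6,000 trials per row. Both used N = 60, 82% retained, 65% women, skewed counts and an effect of 0.8 SD on the latent scale. They differ in details such as the assumed region shares and count distribution. R² = p(1−p)g²/(1 + p(1−p)g²), where p is the share of women and g the gender gap; for g = 0.8, 0.2275 × 0.64 = 0.1456, and 0.1456/1.1456 = 0.13. Simulation error on each power figure is about 0.6 points.

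| Gender gap (SD) | R² | Type I error, plain / stratified | Power, plain / stratified | Change | Set |
|---|---|---|---|---|---|
| 0 | 0 | 5.0 / 5.2% | 71.6 / 70.9% | −0.7 | A |
| 0.2 | 0.01 | 4.5 / 4.6% | 71.9 / 71.6% | −0.3 | B |
| 0.4 | 0.04 | 4.4 / 4.9% | 70.8 / 70.9% | +0.1 | B |
| 0.5 | 0.05 | 4.6 / 5.0% | 71.7 / 73.2% | +1.5 | A |
| 0.6 | 0.08 | 4.2 / 4.5% | 70.6 / 72.2% | +1.6 | B |
| 0.8 | 0.13 | 4.2 / 5.0% | 69.4 / 73.9% | +4.5 | A |
| 0.8 | 0.13 | 4.1 / 5.0% | 67.9 / 72.2% | +4.3 | B |
| 1.0 | 0.19 | 3.6 / 5.0% | 66.2 / 73.7% | +7.5 | A |

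The share of women matters. At 80% women, power is 72.0 / 70.6% with no gap (−1.4) and 70.2 / 74.2% at a gap of 1.0 (+4.0). At 90% women, a gap of 0.8 gives 71.9 / 73.2% (+1.3).

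A further run (4,000 trials per scenario) agrees: a cost of about 1 point or less with no gap, nothing at 0.3 SD, about 2 points at 0.6 SD and about 7 points at 1.0 SD. In that run the Cochran-Mantel-Haenszel test by gender gained about 5 points over chi-squared at 1.0 SD.

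**Step 3: why not all ten cells.** Ten cells for 60 people average six each. A separate simulation (normal outcomes, d = 0.75, no dropout, 80% women) gave:

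| R² | Plain Wilcoxon | van Elteren, ten cells | Linear model, gender + region |
|---|---|---|---|
| 0 | 80% | 73% | 81% |
| 0.10 | 79% | 75% | 83% |
| 0.20 | 82% | 82% | 88% |
| 0.30 | 83% | 87% | 92% |

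On average about 2.2 of the 60 fell in cells containing only one arm and contributed nothing to the ten-cell rank test.

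**The case against.** The strongest objection is that nothing in the documents shows the strata to be prognostic for what is tested. A reader might infer it from the Purpose/Introduction, which reports past-year indoor tanning in 6.5% of women and 1.7% of men. Those figures describe indoor tanning in US adults at large. The SAP tests motivation, outdoor-tanning intentions and outdoor tanning, in people selected because they tanned in the past year and expect to tan again.

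Even taken at face value the figures imply little. On a latent normal scale the thresholds are 1.514 and 2.120, a gap of 0.61 SD before selection. Restricted to those who tanned, about 0.21 SD remains, or roughly 1% of variance with 65% women. At that size the stratified test gains nothing. This objection stands, and it is why the effect must be stated conditionally.

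A reader might also infer that the trial throws away power it had paid for. The documents do not support that: the protocol declines a power analysis, sets 30 per group on feasibility grounds and labels the tanning outcomes exploratory.

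It can also be said that faulting the tests for ignoring the strata and then using gender alone is inconsistent. Part of this stands. Gender alone is a compromise forced by the sparse cells, and additive adjustment for both factors did at least as well as the plain test in step 3.

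Finally, the SAP is written in the past tense, so a change of test may now be post hoc. That affects how the result is labelled, not whether it is worth reporting.

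**Conclusion.** The mismatch between design and analysis is real and unexplained. Its consequence is conditional and small. Over assumed gender gaps of 0 to 1.0 SD, stratifying by gender changes power by about −1 to +7 points. Gains of 4 points or more appear only at gaps of 0.8 SD or above, and at 0.4 SD or below there is no gain. The plain Wilcoxon test's type I error runs from about 5% down to 3.6% over the same range, while the stratified test stays close to 5%. All of this rests on the assumed alpha, block size, retention, share of women and outcome distribution.

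It would be wrong to conclude that the planned tests are invalid or that a primary conclusion is at risk. The error, if there is one, is on the conservative side. The benchmarks of over 80% for retention, participation and acceptability do not use these tests. This is a minor improvement to exploratory comparisons.

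**What to change.** In the SAP:

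- Replace the Wilcoxon rank sum test with the van Elteren test stratified by gender for change in motivation, intentions to tan outdoors and number of times tanned outside.
- Replace the chi-squared test with the Cochran-Mantel-Haenszel test stratified by gender for any outdoor tanning at follow-up.
- Do not stratify on all ten gender-by-region cells, and say that this is because they are too sparse.
- If the unstratified results are already known, keep them as reported and add the stratified tests as a labelled sensitivity analysis.

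The cost is a sentence or two in the SAP and a small change to the SAS code. Gender is known for every randomised participant because allocation depends on it. The downside is about 1 point of power if gender turns out not to be prognostic.
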